7.1.2.5 CRITERIA FOR COMING OFF-TREATMENT

Off-treatment criteria mainly apply to eligibility for repeat Descartes-30 treatments. Patients will be taken off treatment for the following:

- DLT as defined in Section 8.1.2 directly attributable to Descartes-30 cells.
- General or specific changes in the patient's condition rendering the patient ineligible for further treatment in the judgment of the investigator.

7.1.3 RETURN OR DESTRUCTION OF STUDY PRODUCT

7.2 SAFETY MONITORING PERIOD

7.2.1 CONCOMITANT MEDICATIONS

Any medication the patient takes other than the study product between screening and Day 28 (or last day of stay in the administering unit, whichever comes earlier), including herbal and other non-traditional remedies, is considered to be a concomitant medication. All concomitant medications must be recorded in the e-CRF **except for**: nutritional and volume therapy, electrolyte support, vitamins, and supportive therapies such as artificial tears, ointments, etc.

The following information must be recorded in the e-CRF for each concomitant medication: generic name, route of administration, start date, stop date, dosage and indication. If a patient is discharged from the administering unit prior to Day 28 then the patient must be instructed that the Investigator may ask about additional medication up to Day 28.

The choice of concomitant medications or therapies will be left to the Investigator's discretion. The supportive care will be provided based on the local institute's ICU, IMC, and acute care floor standards. Any DNase containing therapy should be avoided unless it is absolutely medically necessary.

7.2.2 MANAGEMENT OF TOXICITIES

The cellular base of Descartes-30 is MSCs, a cell type which has appeared safe for therapeutic use in prior studies including over 2000 patients.³⁹ Toxicities, if any, are expected to occur within several hours of MSC infusion. The largest dataset for guiding expectant toxicity management comes from a meta-analysis of 55 randomized clinical trials.³⁹ The MSC-secreted products are two human DNases that are normally present in serum; that are too bulky to enter cells; and for which the target (extracellular DNA) has no physiologic role in a healthy host. The expression of these DNases is therefore not expected to confer toxicity, although this hypothesis will be tested in this study in the usual cautious and regimented fashion. The guidelines below are recommendations only to manage these potential adverse events and can be tailored to an individual patient's needs based on the judgment of the Investigator or treating physician. Management that differs from these recommendations will not be considered a protocol deviation.

7.2.2.1 FEBRILE REACTION

Within 24 hours of administration, febrile infusion reactions have been reported for MSC infusions with only 6 out of 880 MSC-treated patients having a fever-related SAE.³⁹ To treat ordinary fever, a dose of ≥ 500 mg acetaminophen is recommended. Cooling blankets may be given if fever is greater than 40°C. In the unlikely event that the subject develops sepsis or systemic bacteremia following Descartes-30 cell infusion, appropriate cultures and medical management should be initiated. If a contaminated cell product is suspected, the product can be retested for sterility using archived samples that are stored in the central manufacturing facility.

7.2.2.2 INFUSION REACTION

Infusion-related reactions that occur during or within 24 hours following infusion were reported but not significantly higher than placebo.³⁹ See Section 8.1.2 for definition of infusion reaction for

this study. The management is supportive care as reactions are expected to quickly subside spontaneously.

7.2.2.3 THROMBOEMBOLIC EVENTS

Recent pre-clinical and clinical data demonstrate that MSCs can express or increase secretion of proteins associated with coagulation signals.^{49,50} However, these incident events are rare (17 events in 1112 patients in the meta-analysis³⁹), and were reported in both treatment and control groups with no significant difference associated with administration of MSCs. Thus, these events will likely be rare and as such investigators should evaluate embolic events in their differential diagnosis while managing clinical changes within 24 hours following Descartes-30 infusion.

7.2.2.4 MALIGNANCY/ECTOPIC TISSUE FORMATION

In the pooled analysis of 19 RCTs that reported on malignant transformation and/or ectopic tissue formation, there was no significant increase in the risk of these serious adverse events. However, investigators should instruct the patients to contact the Investigator and/or the Sponsor that there is a theoretical risk of malignancy and therefore patients should report these events if they are diagnosed even after coming off-study.

8 SAFETY ASSESSMENT AND PROCEDURES

8.1 DEFINITIONS

8.1.1 ADVERSE EVENTS (AE)

An adverse event (AE) is defined as any reaction, side effect, or untoward event that occurs during the clinical trial associated with the use of a test article in humans, whether or not the event is considered related to the treatment or clinically significant. For this study, AEs will include events reported by the patient, as well as clinically significant abnormal findings on physical examination or laboratory evaluation. A new illness, symptom, sign or worsening of a pre-existing condition or abnormality is considered an AE. An abnormal laboratory value will be considered an AE if the laboratory abnormality is characterized by any of the following:

- Results in discontinuation from the study.
- Is associated with clinical signs or symptoms.
- Requires treatment or any other therapeutic intervention.
- Is associated with death or another serious adverse event, including hospitalization.
- Is judged by the Investigator to be of significant clinical impact.

All AEs, including clinically significant abnormal findings on laboratory evaluations, regardless of severity, will be followed until satisfactory resolution.

8.1.2 DOSE LIMITING TOXICITY (DLT)

Following reactions within 4 hours of Descartes-30 infusion will be considered as DLT:

1. Addition of a third vasopressor
2. Increase in vasopressor dose over baseline greater than or equal to the following:
 - a. Norepinephrine: 1.5 μ g/kg per min
 - b. Phenylephrine: 100 μ g/kg per min
 - c. Dopamine: 10 μ g/kg per min
 - d. Epinephrine: 1 μ g/kg per min
 - e. Vasopressin: 0.04 IU/min
3. Hypoxemia requiring an increase over baseline in FiO_2 of ≥ 0.2 and/or increase in positive end-expiratory airway pressure level of 5 cm H₂O or more to maintain transcutaneous oxygen saturations in an acceptable range based on PI's discretion
4. New cardiac arrhythmia requiring cardioversion (chemical or electrical)
5. New ventricular tachycardia, ventricular fibrillation, or asystole
6. Death

Also, any Grade 3-5 toxicity probably or definitely attributed to Descartes-30 will be a DLT.

8.1.3 SERIOUS ADVERSE EVENT (SAE)

An adverse event or suspected adverse reaction is considered serious if in the view of the Investigator or the Sponsor it results in any of the following:

- Death
- Infusion reaction defined in Section 8.1.2
- Prolongation of existing hospitalization
- Persistent or significant incapacity or substantial disruption of the ability to conduct normal life functions. Important medical events that may not result in death, be life-threatening, or require hospitalization may be considered a SAE experience when, based upon appropriate medical judgment, they may jeopardize the patient or subject and may require medical or surgical intervention to prevent one of the outcomes listed in this definition.

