8.3.3 FDA NOTIFICATION

The Sponsor is required to report certain study events in an expedited fashion to the FDA. These written notifications of adverse events are referred to as IND safety reports. The sponsor must report an IND safety reports as described in:

<http://www.fda.gov/downloads/Drugs/GuidanceComplianceRegulatoryInformation/Guidances/UCM227351.pdf>

The following describes the safety reporting requirements by timeline for reporting and associated type of event:

- **within 7 Calendar Days** any study event that is unexpected, fatal or life-threatening suspected adverse reaction; or
- **within 15 Calendar Days** any study event that is unexpected, suspected adverse reaction that is serious, but not fatal or life-threatening -or- a previous adverse event that was not initially deemed reportable but is later found to fit the criteria for reporting, any finding from tests in laboratory animals that suggest a significant risk for human subjects including reports of mutagenicity, teratogenicity, or carcinogenicity or reports of significant organ toxicity at or near the expected human exposure.

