9 STATISTICAL CONSIDERATIONS

9.1 SAMPLE SIZE

As this is an early-phase open-label study with a dose-escalation regimen, no formal sample size calculations have been performed. The sample size has been selected for practical considerations and is based upon experience from similar past clinical study designs. The selected number of subjects is considered sufficient to achieve the clinical study objectives, which are not of an inferential statistical nature.

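### Section 8.1.3 does not list life-threatening events or new hospital admission as SAE criteria, so some such events become SAEs only by judgment or through another listed outcome

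*Combined protocol and SAP*

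**What the plan says.** Under 8.1.3, an event "is considered serious if in the view of the Investigator or the Sponsor it results in any of the following". The list has four entries: death; "Infusion reaction defined in Section 8.1.2"; "Prolongation of existing hospitalization"; and persistent or significant incapacity. No redaction or missing figure is marked there. The last entry ends with a clause on other events: "Important medical events that may not result in death, be life-threatening, or require hospitalization may be considered a SAE experience", if medical judgment finds that they put the patient at risk and may need intervention to prevent a listed outcome.

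Four other places bear on the definition:

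- 8.1.1, in saying when an abnormal laboratory value counts as an AE, names hospitalization as an instance of an SAE.
- 8.1.4 is headed as a definition of serious unexpected reactions, but its text defines only what is unexpected.
- 8.3.1 requires the site to notify the sponsor within 24 hours of SAEs and SUSARs, as defined in 8.1.3 and 8.1.4.
- 8.3.3 requires an FDA report within 7 calendar days of "any study event that is unexpected, fatal or life-threatening suspected adverse reaction". Its 15-day class is for serious reactions that are neither fatal nor life-threatening.

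Section 8.2.1 sets the SAE reporting period: from the first infusion to 7 days after the last. After that, an SAE is reported only if judged probably or definitely related to the product.

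**The concern.** The list and the text around it do not match. The important-medical-event sentence is written as a catch-all for events that miss three main criteria: death, threat to life and hospitalization. Of these, only death is on the list; hospitalization appears only as prolongation of a current stay, and threat to life does not appear.

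Two things are at stake. The first is timing. The 24-hour notice is the site-level step that lets the sponsor meet the 7-day FDA deadline. An event not classed as an SAE follows the ordinary AE route in 8.2.1, with e-CRF entry within 3 working days and without the SAE form and narrative of 8.3.1. The second is the safety output. Section 3 makes the description of SAEs part of the primary safety objective. In a multi-center trial, a class of events that depends on a permissive clause can be counted at one site and not at another.

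**Working it through.** No arithmetic underlies the definition. Section 9.1 says that "no formal sample size calculations have been performed", and there is no planned figure to reproduce. The check sets the sections side by side.

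**Step 1. Which criteria are listed, and which are presupposed elsewhere?**

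| Criterion | Listed in 8.1.3? | Presupposed elsewhere? |
|---|---|---|
| Death | Yes | 8.1.3 closing sentence, 8.3.3 |
| Life-threatening | No | 8.1.3 closing sentence; 8.3.3, whose 15-day class treats it as a kind of serious event |
| New inpatient admission | No, prolongation only | 8.1.3 closing sentence; 8.1.1 |

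Both omissions are confirmed, and each conflicts with at least two other statements in the protocol.

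**Step 2. By what route does each kind of event become an SAE?**

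| Event | Route under 8.1.3 | Status |
|---|---|---|
| Fatal event | Death | Listed |
| Non-fatal, life-threatening, meets an 8.1.2 reaction within 4 hours of infusion, such as "New ventricular tachycardia, ventricular fibrillation, or asystole" | Infusion reaction | Listed |
| Non-fatal, life-threatening, prolongs the stay or causes lasting incapacity | Those entries | Listed |
| Related Grade 4 toxicity outside the 4-hour list | Only if the pointer to 8.1.2 means every DLT and not just the timed reactions | Unclear |
| Other non-fatal life-threatening event | Important-medical-event clause | Discretionary |
| Readmission after discharge, with no other listed outcome | Important-medical-event clause | Discretionary |

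**Step 3. Can the discretionary rows occur?** The timed reactions in 8.1.2 cover 4 hours. Sections 7.2.2.2 and 7.2.2.3 direct attention to infusion-related and embolic events over 24 hours, so 24 − 4 = 20 of those hours lie outside the timed list. A non-fatal embolic event at hour 10 that resolves without demonstrably lengthening an ICU stay is an example. As for readmission, 6.5 provides for patients discharged before Day 14, and PNA Cohort patients may be treated on an acute care floor (Schedule of Activities, footnote w).

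**Step 4. How far does the readmission gap reach?** On the planned schedule the last infusion is on Day 2, so the general SAE window closes at Day 2 + 7 = Day 9, or later if infusions are delayed. From Day 9 to the Day 90 contact, 90 − 9 = 81 days, only SAEs judged probably or definitely related are reported. A new-admission criterion would therefore change reporting only for readmissions up to about Day 9 and for later related ones. The same limit applies to late life-threatening events.

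**Step 5. Does 8.1.4 supply the missing criterion?** It tests only whether an event is unexpected. Its heading requires the event to be serious as well, and the only definition of serious is in 8.1.3. The SUSAR route therefore rests on the same incomplete list.

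**The case against.** The strongest reply is that the gap lies between listed and judged classification and does not exclude any event. The opening words of 8.1.3 already rest on the view of the investigator or sponsor, and a life-threatening event fits the important-medical-event test almost by nature. That is fair, and it limits the point. It does not remove it, because the clause is permissive and the other entries are not.

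A second reply is that 8.1.4, read literally, sends any unexpected suspected reaction to the sponsor, including a life-threatening one. Step 5 shows why this cannot be relied on: the section borrows its meaning of serious from 8.1.3.

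Three stronger readings are tempting, and the documents support none of them.

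- A reader might infer that the events in the 7-day class of 8.3.3 are not SAEs. Fatal ones are, and many non-fatal ones enter through 8.1.2 or a prolonged stay. Section 8.3.3 is also a separate sponsor duty that does not cite 8.1.3. The duty stands; what is weakened is the site notice that feeds it.
- A reader might infer that every readmission to Day 90, potentially in all survivors among about 36 patients, is lost through this definition. For most later readmissions the binding limit is 8.2.1, and they would stay outside SAE reporting even after the fix.
- A reader might infer that the primary endpoint is at risk. The MTD rests on DLTs, which do not depend on 8.1.3. A missed SAE would still meet the AE definition and be tabulated under 9.2, and in Arm 1 the investigator and Medical Monitor review each patient by Day 7. This backstop is only partial in Arm 2, where AEs more than 7 days after the last infusion are also reported only if judged related.

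**Conclusion.** The definition is wrong as written, by the protocol's own text: 8.1.3 omits two criteria that its closing sentence presupposes, one of which 8.1.1 also presupposes and the other 8.3.3. The consequence is narrower than the omission first suggests. It concerns non-fatal life-threatening events outside the 8.1.2 four-hour reactions, and readmissions that are early (within 7 days of the last infusion) or judged probably or definitely related. These are SAEs only by discretion or through another listed outcome, so they may miss the 24-hour notice and may be counted inconsistently.

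How many events this would affect cannot be derived from the documents, which give no expected rates. The conclusion assumes that the infusion-reaction entry means the timed reactions in 8.1.2. If it means every DLT, related Grade 4 toxicity is also covered and the gap is smaller, but it does not close: events judged less than probably related, and readmissions not tied to a related Grade 3 to 5 toxicity, would remain.

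**What to change.** Add two entries to the list in 8.1.3: that the event is life-threatening, and that it requires new inpatient hospitalization. Then reconcile 8.1.1, 8.1.3, 8.1.4, 8.3.1 and 8.3.3 so that all five use one set of seriousness criteria. In doing so, state in 8.1.4 that a SUSAR must meet the 8.1.3 criteria, and say in 8.1.3 whether the pointer to 8.1.2 covers only the timed reactions or every DLT.

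The cost is two lines, a few cross-references, and some additional SAE forms in a population that is largely in intensive care. The change affects a reporting definition only. It does not by itself widen the reporting period in 8.2.1, so the sponsor should not expect it to capture late readmissions that are not judged related.

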8.1.4 SERIOUS UNEXPECTED ADVERSE REACTION (SUSAR)

An adverse event or suspected adverse reaction is considered "unexpected" if it is not listed in the Investigator Brochure or is not listed at the specificity or severity that has been observed; or, if an Investigator Brochure is not required or available, is not consistent with the risk information described in the general investigational plan or elsewhere in the current application.

"Unexpected" also refers to adverse events or suspected adverse reactions that are mentioned in the Investigator Brochure as occurring with a class of the test article or as anticipated from the pharmacological properties of the drug but are not specifically mentioned as occurring with the test article under investigation.

8.2 RECORDING OF ADVERSE EVENTS

8.2.1 ADVERSE EVENT RECORDING

The adverse event recording period for this study starts after patient or legal representative signs consent and ends at Day 90 visit or when patient comes **off-study based on criteria in Section 8.4**. For SAE and SUSAR, reporting period starts with first Descartes-30 infusion and ends 7 days after last infusion. After 7 days, an AE (only in Arm 2), SAE (both Arms) or SUSAR (both Arms) is **only reported if it is probably or definitely attributed to Descartes-30 infusion**. At each contact with the subject during the adverse event recording period, the Investigator or his/her designee must seek information on adverse events by specific questioning and, as appropriate, by examination. Information on all adverse events should be recorded immediately in the source document, and in the appropriate adverse event module of the case report form (CRF). All clearly related signs, symptoms, and abnormal diagnostic procedures results should be recorded in the source document, though it should be grouped under one diagnosis.

All adverse events should be treated appropriately. If a concomitant medication or non-drug therapy is given, this action should be recorded on the Adverse Event CRF. Adverse events should be entered into the e-CRF system within 3 working days from the knowledge of the event took place. Once an adverse event is detected, it should be followed until its resolution or until it is judged to be permanent, and assessment should be made at each visit (or more frequently, if necessary) of any changes in severity, the suspected relationship to the study treatment, the interventions required to treat it, and the outcome.

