5.3 SCREEN FAILURES

[figure not shown]
Screen failures are defined as subjects who consent to participate in the clinical study but never receive Descartes-30 cells. A minimal set of screen failure information is required including demography and screen failure details. Screen failure data will not be recorded within the Case Report Form (CRF).

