- Research blood collection: All protocol required research blood collection assessments must be conducted in accordance with Laboratory Manual, and the Schedule of Activities. Laboratory requisition forms must be completed, and samples must be clearly labelled with the subject number, protocol number, site number, and visit date. Details for the preparation and shipment of samples will be provided by the laboratory and are detailed in the Laboratory Manual. Reference ranges for all safety parameters will be provided to the site by the laboratory responsible for the assessments.
- Exploratory Bronchoalveolar lavage, Tracheal Aspirate or sputum (induced or expectorated): Optional based on PI's discretion. See Schedule of Activities (Section 1)

and Laboratory Manual for more details. Should be done per institute's standards of operations (alternatively it can be done on Day 0 before infusion)

- Chest Imaging: CT scan or Chest X-Ray (alternatively it can be done on Day 0 before infusion)
- AE review and evaluation: AE collection starts after consent is signed.
- APACHE II Score: See [Appendix A](#) for APACHE II score.
- Clinical End-point Assessment includes: Survival (Y/N), On mechanical ventilation (Y/N), In ICU (Y/N), In Hospital (Y/N), Use of anti-coagulation (drug, dose, intent: prophylaxis vs therapeutic), WHO Ordinal Score (See Appendix D for scale). If patient is in ICU then the following assessment will be completed: Sequential Organ Failure Assessment (SOFA, See [Appendix B](#) for template form), PaO₂/FiO₂, following ventilation parameters (as applicable): type of ventilation (CPAP, BiPAP, or intubation)/ ventilation rate/ pulse/ tidal volume/ positive end-expiratory pressure (PEEP), recording of vasoactive drugs and renal support, recording of supportive interventions that can impact clinical endpoints (use of prone ventilation, use of paralytics, use of pulmonary vasodilators, use of corticosteroids, use of oral decontamination and raising the head of the patient to at least 30° to prevent ventilator-associated pneumonia).

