7.1.2 DOSING AND ADMINISTRATION

7.1.2.1 PRE-INFUSION MONITORING AND DELAY OF CELL INFUSION

[figure not shown]
Infusions can be delayed up to 96 hours based on PI discretion. Prior to all Descartes-30 infusions, patients should be observed for 2 hours (\pm 30 min) to document their stability by meeting the following parameters and based on PI's best clinical judgement:

1. Patient is not requiring a change in ventilator settings
2. Stable use of vasopressors if the patient required vasopressors for blood pressure support.
Stable use is defined as increasing no more than 50% of baseline recorded at initiation of monitoring.

During 2-hour monitoring, following parameters should be recorded at least every 30 min: ventilation variables [type of ventilation (CPAP, BiPAP, or intubation), ventilation rate, pulse, tidal volume, positive end-expiratory pressure (PEEP)], recording of vasoactive drugs and renal support and vital signs [include core temperature, mean arterial pressure (mmHg), pulse (beats/min), respiratory rate (breaths/min)]. If patients do not meet stability criteria for 2 hours, infusion can be delayed for up to 96 hours. If infusion is delayed, the patient will be periodically monitored to assess stability. If infusion is delayed more than 96 hours due to medical instability, patients will come off study treatment. Infusions can also be delayed up to 96 hours in case of a holiday or by PI's discretion.

Patients experiencing toxicities that are probably or definitely related to Descartes-30 will have their next Descartes-30 dose delayed until these toxicities have resolved to at least Grade 2, unless in the documented opinion of the site Principal Investigator and the medical monitor it is reasonable to proceed. During this period, patients will be assessed to record adverse events and decide whether the patient meets criteria for cell infusion. The discussions between the Medical Monitor and site Principal Investigator will be documented. If a dose is delayed for more than 96 hours, the patient will come off study treatment.

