8.3 SAE AND SUSAR REPORTING

To ensure patient safety, every SAE and SUSAR, regardless of suspected causality, occurring during the adverse event reporting period defined in Section 8.2.1 must be reported to the Sponsor within 24 hours of learning of its occurrence. Recurrent episodes, complications, or progression of the initial SAE must be reported as follow-up information is received. An SAE occurring at a different time interval or otherwise considered completely unrelated to a previously reported one should be reported separately as a new event.

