16.4.1 SCREENING

All inclusion and exclusion criteria will be reviewed by the Investigator or qualified designee at the Screening Visit to ensure that the subject qualifies for the study. All inclusion criteria must be met, and none of the exclusion criteria may apply. Subjects found ineligible during the review of inclusion/exclusion will not proceed through the remaining screening process.

- Informed consent
- Demographics, Medical History
- Concomitant medications
- Research blood collection: All protocol required research blood collection assessments must be conducted in accordance with the Laboratory Manual and the Schedule of Activities. Laboratory requisition forms must be completed, and samples must be clearly labeled with the subject number, protocol number, site number, and visit date. Details for the preparation and shipment of samples will be provided by the laboratory and are detailed in the Laboratory Manual.
- Exploratory Bronchoalveolar lavage: See Laboratory Manual for more details. Should be done per 'institute's standards of operations. If BAL can not be performed then tracheal aspirate.
- Clinical End-point Assessment includes: Survival (Y/N), On mechanical ventilation (Y/N), In ICU (Y/N), In Hospital (Y/N), Use of anti-coagulation (drug, dose, intent: prophylaxis vs therapeutic), WHO Ordinal Score (See Appendix D for scale). If patient is in ICU then the following assessment will be completed: Sequential Organ Failure Assessment (SOFA, See [Appendix B](#) for template form), PaO₂/FiO₂, following ventilation parameters (as applicable): type of ventilation (CPAP, BiPAP, or intubation)/ ventilation rate/ pulse/ tidal volume/ positive end-expiratory pressure (PEEP), recording of vasoactive drugs and renal support, recording of supportive interventions that can impact clinical end-points (use of prone ventilation, use of paralytics, use of pulmonary vasodilators, use of corticosteroids, use of oral decontamination and raising the head of the patient to at least 30° to prevent ventilator-associated pneumonia).
- CBC with differential: Only if performed as Standard of Care.
- Serum chemistry: Only if performed as Standard of Care. Chemistry includes: Glucose, Ca, Mg, Phos, ALP, Albumin, Total Protein, Total Bilirubin, K, Na, Cl, HCO₃, BUN, Cr, ALT, AST, LDH, Amylase.
- CRP, ferritin, D-Dimer:
- PT/INR, PTT: If performed as Standard of Care.
- Chest Imaging: CT scan (preferred) or Chest X-Ray.

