16.4.2 DAY 1,2,3

On each day, the following assessments should be completed. There should be at least 12 hours between each assessment. Assessments after Day 1 are omitted if the patient is discharged from ICU.

- Concomitant medications
- Clinical End-point Assessment includes: Survival (Y/N), On mechanical ventilation (Y/N), In ICU (Y/N), In Hospital (Y/N), Use of anti-coagulation (drug, dose, intent: prophylaxis vs therapeutic), WHO Ordinal Score (See Appendix D for scale). If patient is in ICU then the following assessment will be completed: Sequential Organ Failure Assessment (SOFA, See [Appendix B](#) for template form), PaO₂/FiO₂, following ventilation parameters (as applicable): type of ventilation (CPAP, BiPAP, or intubation)/ ventilation rate/ pulse/ tidal volume/ positive end-expiratory pressure (PEEP), recording of vasoactive drugs and renal support, recording of supportive interventions that can impact clinical end-points (use of prone ventilation, use of paralytics, use of pulmonary vasodilators, use of corticosteroids, use of oral decontamination and raising the head of the patient to at least 30° to prevent ventilator-associated pneumonia).
- Research blood collection: All protocol required research blood collection assessments must be conducted in accordance with Laboratory Manual.
- Exploratory Bronchoalveolar lavage: **This should be done only once during this period.** There should be at least 48h passed since the collection for Screening Visit (Section 16.4.1). If BAL can not be performed, then tracheal aspirate.
- CBC with differential: Only if performed as Standard of Care.
- Serum chemistry: Only if performed as Standard of Care. Chemistry includes: Glucose, Ca, Mg, Phos, ALP, Albumin, Total Protein, Total Bilirubin, K, Na, Cl, HCO₃, BUN, Cr, ALT, AST, LDH, Amylase.
- CRP, ferritin, D-Dimer.
- PT/INR, PTT: If performed as Standard of Care.

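### Serious harm from a research lavage done before the first infusion falls outside the SAE reporting window, and the plan contradicts itself on where AEs of never-dosed patients are recorded

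*Combined protocol and SAP*

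**What the plan says.** Section 8.2.1 sets two windows. For adverse events in general: "The adverse event recording period for this study starts after patient or legal representative signs consent and ends at Day 90 visit" (or at off-study). For serious events: "For SAE and SUSAR, reporting period starts with first Descartes-30 infusion and ends 7 days after last infusion". Section 6.1 agrees with the first window: "AE collection starts after consent is signed". Section 8.3 limits the expedited duty to events "occurring during the adverse event reporting period defined in Section 8.2.1 must be reported to the Sponsor within 24 hours".

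Section 6.1 lists an exploratory BAL, tracheal aspirate or sputum sample at screening, at the investigator's discretion, and allows it on Day 0 before infusion instead.

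Section 5.3 defines a screen failure as anyone who consents but never receives the cells. It requires a minimal data set (demography and the failure details) and then says: "Screen failure data will not be recorded within the Case Report Form (CRF". Section 7.1.2.1 describes one way a consented patient can end up undosed: "If infusion is delayed more than 96 hours due to medical instability, patients will come off study treatment".

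In Appendix E, Section 16.4.1 lists a BAL at screening without calling it optional, with a substitute: "If BAL can not be performed then tracheal aspirate". Section 16.4.2 allows one further lavage on Days 1-3, subject to spacing: "There should be at least 48h passed since the collection for Screening Visit". Section 16.4.3 moves it to Days 4-6 if it has not been done by then.

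**The concern.** BAL is an invasive step that the trial itself adds in patients with ARDS or severe pneumonia, and the primary objective is safety. If a patient has a serious complication of the lavage before the first infusion, the reporting rule does not require the sponsor to be told within 24 hours. If that patient is then not dosed, one section directs the event to the CRF and another keeps it out. At stake are the speed with which the sponsor and medical monitor learn of serious harm from a research procedure and, for consented but undosed patients, whether the event reaches the trial database at all.

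**Working it through.** No arithmetic underlies the point and the plan states no figure to reproduce. The check sets the rules side by side.

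**1. Windows against the timing of the lavage**

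| Item | Opens | Closes | Source |
|---|---|---|---|
| AE recording | Signed consent | Day 90 or off-study | 8.2.1, 6.1 |
| SAE/SUSAR reporting | First infusion | 7 days after last infusion | 8.2.1 |
| 24-hour sponsor report | As the 8.2.1 reporting period | As the 8.2.1 reporting period | 8.3 |
| First research BAL (optional) | Screening | Day 0, before infusion | 6.1 |

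The first lavage lies wholly inside the AE window and wholly before the SAE window. Section 8.2.1 uses the word recording for AEs and reporting for SAEs and SUSARs, so the period that 8.3 points to is the one that opens at first infusion.

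**2. Which lavage is affected**

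Section 6.3 asks for a repeat on Days 3-6 if one was done before treatment. With all three infusions on schedule, the SAE window closes on Day 2 + 7 = Day 9. Even if only the Day 0 infusion is given, it closes on Day 0 + 7 = Day 7. The Days 3-6 lavage is therefore covered, and only the pre-infusion procedure is exposed.

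**3. Length of the gap**

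- Shortest: the same day, because screening and the Day 0 infusion may coincide (Section 1, note j).
- Longest: 7 days for pneumonia or 14 days for ARDS (Synopsis, Study Design). These limits run from diagnosis. The lavage follows diagnosis and consent, so they are upper bounds on the time from lavage to infusion.
- Never dosed: the SAE window does not open.

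**4. The undosed patient**

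The pre-infusion stability check in 7.1.2.1 applies to every infusion, including the first. A patient who is unstable beyond 96 hours (4 days) before the first infusion comes off treatment undosed and so meets the 5.3 definition of a screen failure. Section 8.2.1 sends all AEs from consent to the source record and the CRF AE module; Section 5.3 excludes screen-failure data from the CRF. A site cannot follow both.

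**5. Appendix E**

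The main schedule in Section 1 has a row for AE review. The Appendix E schedule (16.3) and the lists in 16.4.1 to 16.4.4 have none, although they include BAL at screening and once more on Days 1-3 or 4-6. Untreated controls have no first infusion, so the 8.2.1 SAE window cannot open for them. The opening of Appendix E is not available in the text reviewed, and later parts are redacted.

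**The case against.** The strongest reply is that the event is not lost. In a patient who is later dosed, a complication of the lavage is an AE from consent, AE review is scheduled at screening, and e-CRF entry is due within 3 working days. In Arm 1 the investigator and medical monitor review the data at Day 7 or the last day in the unit. Section 8.3.2 sends deaths during the study to the IRB with no first-infusion condition. Section 8.3.1 repeats the 24-hour duty without naming a window, and 8.3 speaks of the adverse event reporting period, so a cautious site might report from consent anyway. In the main study the lavage is optional, with aspirate or sputum as alternatives.

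Most of this stands and limits the point. It does not remove it: 8.2.1 is the only place that defines the SAE period, and it does so explicitly. A site that follows it exactly owes no expedited report before infusion.

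A reader might infer more than the documents support:

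- *That the sponsor, medical monitor and IRB cannot see procedure harm, and that the AE tables understate it.* For patients later dosed, what is missing is the expedited report, not the record. Under-counting can arise only among the never-dosed.
- *That about 36 patients, each with two lavages, are exposed.* The lavage is optional and the second falls inside the SAE window, so about 36 (Synopsis) is no more than a ceiling on treated patients with a pre-infusion lavage.
- *That the patients most harmed are systematically removed.* This needs a lavage to be chosen, a serious complication, a failed stability check and instability beyond 96 hours. It is possible, but no rate is given for any step. Section 5.3 also keeps a minimal record, and source documents remain.
- *That Appendix E has no safety reporting.* Only the visible schedule and procedure lists can be said to lack it.

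**Conclusion.** The point holds for two rules. First, a serious complication of a research procedure between consent and first infusion falls outside the period to which 8.2.1 and 8.3 attach the 24-hour report. Second, 5.3 and 8.2.1 contradict each other on whether AEs of consented but undosed patients enter the CRF. Both conclusions are firm on the current text, taking 8.2.1 as the governing definition of the SAE period.

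The size is modest and cannot be put as a rate. Those affected are patients who have a pre-infusion research procedure, plus any consented but undosed patient with an AE for the CRF conflict. The documents give neither their number nor a complication rate.

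The Appendix E part is a query with lower confidence, because relevant text may lie in the part that could not be read. The change should be made: safety is the primary objective and the remedy is small.

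**What to change.** 1. **Section 8.2.1:** start SAE reporting at consent. If the sponsor wants to limit the load, restrict it before first infusion to SAEs related to a protocol procedure (BAL, sputum induction, research blood draw). Align 8.3 and 8.3.1 so that all three sections name the same period. If the restricted version is chosen, the SAE form needs a relation-to-procedure item, because 8.3.1 asks only about the association with study treatment.
2. **Section 5.3:** require AEs and SAEs from consent to be entered in the existing CRF AE form for consented but undosed patients, so that it agrees with 8.2.1.
3. **Appendix E (query):** confirm that SAEs related to research procedures in controls are reported to the sponsor by the 8.3 route. If they are not, add this, with a start point that does not depend on an infusion.

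Items 1 and 2 are wording changes with a small amount of extra data entry; they add no procedure and leave the treatment rules as they are. Item 3 costs nothing if the route already exists. If it does not, checking controls for events is new work in a schedule that shows none, so it should be sized to the procedures performed.
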